## **2.2 RESEARCH ELIGIBILITY EVALUATION**

Pre-treatment blood tests should be performed within two weeks and imaging studies **within 4 weeks prior to enrollment** on the trial unless otherwise stated. The evaluations required prior to starting treatment are listed in table form in **Appendix 2: Study Calendar**.

- Complete history and physical examination including assessment of vital signs and ECOG status
- Laboratory
  - ROUTINE LABS: complete blood count, differential, LDH, SGPT (ALT), SGOT (AST), alkaline phosphatase, bilirubin (total and direct), BUN, creatinine, amylase, lipase, electrolytes, ionized calcium, magnesium, phosphorus, uric acid, albumin and thyroid panel.
    - DMET genotyping of PBMC for ABCB4/ABCB11/RALBP/ CYP8B1 SNPs (to be performed by the CLIA Molecular Diagnostics Laboratory (CLIA #21D0947274) through [name] [name]'s lab under study 06C0014). (**May be performed at any time prior to enrollment**)
  - Urinalysis.
  - Women of child-bearing potential will have a urine or serum  $\beta$ hCG pregnancy test. *Note: this test is to be done within 2 days prior to start of treatment.*

- Coagulation Studies: PT/PTT/Thrombin Time/Fibrinogen, PFA-100, VWF antigen, VWF activity, Factor VIII activity, D-dimer, Fibrin degradation products and FXIII activity, lupus anticoagulant (LA) test
- Radiographic Evaluation
  - Assessment of disease sites by appropriate radiological evaluation. This should include a CT scan of chest, abdomen and pelvis, brain MR, PET-CT, and other standard-of-care imaging specific for each patient’s malignancy.
- Cardiac Function Studies
  - Assessment of cardiac function (ejection fraction/shortening fraction) must be performed within 4 weeks of enrollment by MUGA, Echocardiogram, or cardiac MR to rule out cardiomyopathy.
  - A 12-Lead electrocardiogram (EKG) will also be performed.
- Pathologic/Tissue Evaluation
  - Histologic confirmation of tumor by the NCI Laboratory of Clinical Pathology, NIH (may be performed at any time prior to registration).

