#### **1.3.4 Recent Experience with Mithramycin in Adult Oncology Patients at the NCI**

Twelve patients (10 males; 2 females; median age 51y; range 40-72y) with refractory thoracic malignancies (six MPMs, 2 esophageal cancers, two lung cancers, 2 synovial sarcomas) received 6h mithramycin infusions q day x 7, every 28 days. Response rates following two cycles, pharmacokinetics, and systemic toxicities (cycle 1) were evaluated. A total of 20 cycles were administered to 12 patients; all were evaluable for toxicities. No objective responses were observed in 7 patients who were evaluable for treatment responses. No myelosuppression, uncontrollable nausea or vomiting was observed. No patients experienced bleeding. The lack of these toxicities, which have been associated with mithramycin treatment  may be attributable at least in part to higher purity of the current drug relative to what had been used previously.

Eight patients experienced transient, asymptomatic dose-limiting transaminitis following 25mcg/kg/infusions. This toxicity always occurred on day 4 of the infusion. Percutaneous biopsies from three individuals revealed apoptotic hepatocellular death (**Figure 6A**). Four patients (two with MPM) had no hepatotoxicity and tolerated dose escalation to 30 mcg/kg/infusion. Peak and steady state mithramycin levels were 20 and 8nM, respectively, which were not different in patients with or without hepatotoxicity (**Figure 6B**). DMET genotyping revealed that two SNPs (rs2302387 and rs4668115) in genes encoding two related bile transporters (ABCB4 and ABCB11, respectively) were significantly associated with LFT elevations in the 12 patients treated with mithramycin (**Figure 7A** and **Figure 7B**).

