## **3 STUDY IMPLEMENTATION**

### **3.1 STUDY DESIGN**

This study will be conducted as a single site, phase II trial utilizing a Simon Optimal Design. Patients will be analyzed in two cohorts on the basis of primary thoracic malignancy vs. extra-thoracic malignancy metastatic to lungs, pleura or mediastinum. The goal of the study is to determine response rates, pharmacokinetics and molecular responses following 6h mithramycin infusions as a prelude to combinatorial studies as well as protocols utilizing 24h continuous infusions targeting pharmacodynamic endpoints in tumor tissues.

Patients will undergo eligibility evaluation in the Thoracic Surgery Clinic (OP-3). Patients deemed eligible for therapy will sign an informed consent and receive mithramycin as described in Section 3.2. Patients may continue to receive mithramycin as long as they tolerate drug and do not have progressive disease (Section 6.4).

Patients on study will be closely monitored for the development of toxicities using regular physical examinations, blood pressure monitoring, and laboratory evaluations with particular attention to the development of any signs of bleeding. Patients will be admitted to the hospital for the first treatment cycle to allow for close monitoring of toxicities. For subsequent cycles, local patients may receive infusions in the day hospital; patients traveling from out-of-town will be admitted to the hospital. Two weeks (plus 12 or minus 3 days) following each course of therapy (three 21-day cycles) patients will undergo appropriate staging studies to determine response to therapy using RECIST criteria.

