#### **3.5.2 Monitoring During Treatment:**

- Physical exam, to include vital signs, weight, toxicity evaluation and ECOG status within 4 days of each treatment cycle.
- Toxicity assessment during cycles 1 and 2: daily during treatment and then weekly. During cycle 3 and subsequent cycles, twice weekly during treatment and then weekly.
- Laboratory evaluations:
  - CBC with differential count within 2 days prior to treatment and daily during drug administration (days 1-7 prior to each infusion, active treatment week); then twice weekly on off-treatment weeks of cycles 1-2. During subsequent cycles: CBC with differential count within 2 days prior to commencing treatment and twice weekly during administration prior to infusion, then weekly.
  - Chemistry: sodium, potassium, chloride, CO2, creatinine, glucose, BUN, albumin, ionized calcium\*, magnesium, alkaline phosphatase, ALT/GPT, AST/GOT, total bilirubin, total protein daily within 2 days of commencing treatment and during drug administration (days 1-7 prior to each infusion, active treatment week); then twice weekly on off-treatment weeks of cycles 1-2. During subsequent cycles chemistries are performed weekly.
  - Coagulation Studies: PT/PTT/Thrombin Time, Fibrinogen prior to day 1 and on days +4 and +8 of every cycle.
  - Total and fractionated bile acids within 2 days prior to and on day +7 of every treatment cycle and at time of treatment evaluation at the end of the 3rd cycle of therapy.

**Note:** The patient may have evaluations and lab work obtained through his or her local physician between cycles and have the results faxed to the Research Nurse. The Research RN will contact the patient as noted above to discuss toxicity.

\* Ionized calcium is not part of a standard lab panel and could be omitted if not available or not covered by insurance when performed outside NIH.

- 12-Lead EKG:
  - Cycles 1 and 2: Days 1, 4, and 7, before infusion within 1 hour of pre infusion PK sample to evaluate for QT prolongation potential

**Note:** although it is preferable to have the EKGs done within 1 hour of PK sample collection, EKGs may be done outside of the specified times if unexpected events in clinic or floor prevent staff from conducting the study within the specified timeframe. EKGs performed outside of this window will NOT be considered protocol deviations.

- Cycle 3 and subsequent cycles: Within 1 hour of start of infusion on day 1 and day 7.

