### **3.5.4 Follow-up Evaluations:**

After completion the last treatment cycle (See section [3.4](#) for criteria for retreatment), patients will be monitored weekly until all clinically significant toxicities resolve to less than or equal to grade 1 or baseline as follows:

- Toxicity Evaluation
- Laboratory evaluation: CBC, Chem20 equivalent including ionized calcium\*, PT/PTT
- For patients with stable disease or responding to therapy, the following will be done every 2 months until off study criteria are met:
  - History and physical exam
  - Laboratory evaluation: CBC, Chem20 equivalent including ionized calcium\*, PT/PTT
  - Tumor Measurements: CT scan of the chest, abdomen and pelvis as well as PET/CT and brain MR or CT scan.

Note: The patient may have evaluations and lab work obtained through his or her local physician during follow up.

\* Ionized calcium is not part of a standard lab panel and could be omitted if not available or not covered by insurance when performed outside NIH.

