13.3.2 Appendix 2: Study Calendar

		Cycles 1 and 2							
Research Eligibility Evaluation/Baseline		Week 1							Week 2
		day 1	day 2	day 3	day 4	day 5	day 6	day 7	
Mithramycin		x	x	x	x	x	x	x	
Histologic path confirmation	x								
ABCB4 and ABCB11 status	X								
Informed consent	x								
Medical history	x								
Concurrent meds	x								
Physical examination	x	x i							
Performance status	x	x i							
General labs	x	x	x	x	x	x	x	x	xx b
Serum bile acids (total and fractionated)	x	x						x	
Coagulation labs	x				x				x c
Pregnancy test	x								
Cardiac function tests	x								
Imaging studies incl liver Elastograpy by ultrasound	x								
Adverse events		←—————→							
Tumor biopsy	x								
Research labs		x d							x c
PK	x	x df	x df		x df			x df	x g
EKG	X	x d			x d			x d	

		Cycles 3 and beyond*						
		Week 1					Week 2	
		day 1	day 2	day 3	day 4	day 5	day 6	day 7
Mithramycin		x	x	x	x	x	x	x
Histologic path confirmation								
Informed consent								
Medical history								
Concurrent meds								
Physical examination		x i						

**Abbreviated Title:** Mithramycin for Cancer Stem Cells

**Version Date:** 09/14/2018

	Cycles 3 and beyond*							
	Week 1							Week 2
	day 1	day 2	day 3	day 4	day 5	day 6	day 7	
Performance status	x i							
General labs				x h			x	x a
Coagulation labs				x				x c
Serum bile acids (total and fractionated)	x						x	x e (course 1 only)
Pregnancy test								
Cardiac function tests								
Imaging studies including liver elastography by ultrasound								x e
Adverse events								
Tumor biopsy								
Research labs	x d							x c
EKG	x d						x d	
a - once weekly								
b - twice weekly								
c - day 8 of cycle (same as day 1 of week 2)								
d -prior to dosing								
e – two weeks (plus 12 or minus 3 days ) after the end of each course (1 course = 3 cycles)								
f - end of infusion								
g - 24 and 48 hours after day 7 infusion								
h- CBC with differential only								
i – within 4 days prior to the start of each cycle								
*Patients will continue to receive treatment until criteria for removal from protocol or off-study criteria are met (See section 3.6)								

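### The only scheduled pregnancy test precedes cycle 1, while dosing is open-ended and a pregnancy must stop it: a low-frequency safety gap that one repeat test per cycle would close

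*Combined protocol and SAP*

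**What the plan says.** Section 2.2 lists a urine or serum beta-hCG among the pre-treatment laboratory tests for women of child-bearing potential and fixes its timing: "this test is to be done within 2 days prior to start of treatment". The "Pregnancy test" row of Appendix 2 carries one mark, in the baseline column. The row appears again in the table for cycle 3 onward, with no mark.

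Section 3.5.2 sets out laboratory monitoring on treatment: blood counts, chemistry, coagulation and bile acids. Pregnancy testing is not among them. Neither the research evaluations in 3.5.3 nor the follow-up list in 3.5.4 ("Laboratory evaluation: CBC, Chem20 equivalent including ionized calcium", with PT/PTT) includes it.

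Treatment has no fixed end. Section 3.1 states: "Patients may continue to receive mithramycin as long as they tolerate drug and do not have progressive disease". Cycles are seven daily infusions repeated every 21 days (+7/-3), three cycles to a course (3.2).

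The protocol recognizes the hazard. Pregnancy is an exclusion because of fetal risk (2.1.2.8), section 7.3.2.1 treats the agent as possibly teratogenic, and both 3.6.1 and 7.3.2.1 require immediate discontinuation. Section 2.1.1.11 requires contraception during treatment and for two months afterwards.

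**The concern.** A rule that stops treatment for pregnancy can act only once the pregnancy is known. The plan looks for pregnancy once, just before the first infusion, and then relies on the patient or clinician suspecting it. If the schedule is followed as written, a pregnancy that begins after cycle 1 starts could pass through one or more further seven-day cycles before anyone has reason to test. What is at stake is avoidable fetal exposure and a delay in applying the protocol's own discontinuation and reporting rules.

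**Working it through.** **Where a repeat test could have been scheduled**

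| Place | Content | Pregnancy test? |
|---|---|---|
| 2.2 | Pre-treatment evaluation | Yes, once, before cycle 1 |
| 3.4 | Conditions for the next course | None named; the patient must not have met a removal criterion |
| 3.5.2 | Monitoring on treatment | None |
| 3.5.3 | Research evaluations | None |
| 3.5.4 | Follow-up | None |
| Appendix 2 | Calendar | Baseline mark only |
| Appendix 7 | Laboratory list for the local physician | None in the part available |

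The calendar is supporting evidence only, because it is incomplete elsewhere: it omits the cycle 2 day 8 biopsy that 3.5.3 requires. The conclusion rests on the text sections.

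**Infusions given in cycles with no scheduled test** (7 per cycle; only cycle 1 is preceded by a test)

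- Stops after cycle 1: 0 of 7.
- Stops after cycle 2: 14 - 7 = 7 of 14.
- Completes course 1: 21 - 7 = 14 of 21.

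These counts describe the schedule. They do not estimate fetal exposure.

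**Age of the only test**

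Inputs: the test is 0 to 2 days before cycle 1 day 1 (2.2), and the cycle interval is 21 days, -3/+7, so 18 to 28 days (3.2).

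- Cycle 2 day 1: from 18 + 0 = 18 to 28 + 2 = 30 days (nominal 21 to 23).
- Cycle 3 day 7: from 2 × 18 + 6 = 42 to 2 × 28 + 6 + 2 = 64 days (nominal 48 to 50).

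**How often patients go past cycle 1**

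The only data are in 1.3.4: "A total of 20 cycles were administered to 12 patients". The mean is 20/12 = 1.67 cycles. If every patient began cycle 1, then 20 - 12 = 8 cycles, or 8/20 = 40%, came later. This is a rough guide at best. Those patients had 28-day cycles, were not selected by genotype and had response assessed after two cycles, and eight of them had dose-limiting transaminitis.

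**Number of women**

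Two of those 12 patients were women, and ages in the whole group ran from 40 to 72. Eligibility starts at 18 and includes germ cell tumors and sarcomas, so younger women can enter. The documents give neither the number of women of child-bearing potential nor a pregnancy risk under contraception, so no expected count can be derived.

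**Whether a repeat would need a new visit**

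It would not. Section 3.5.2 already calls for "CBC with differential count within 2 days prior to treatment and daily during drug administration" in cycles 1 and 2, for "CBC with differential count within 2 days prior to commencing treatment and twice weekly during administration prior to infusion" in later cycles, and for "Total and fractionated bile acids within 2 days prior to and on day +7 of every treatment cycle". Each gives a blood draw in the two days before a cycle.

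**The case against.** The strongest reply is that 3.4 already deals with this. A further course requires that no removal criterion has been met, and pregnancy is such a criterion. That stands, and a reader who infers that the protocol would knowingly allow a pregnant woman to be re-treated is wrong. But the condition comes with no test, and it is written for the next course, so it adds nothing before cycles 2 and 3.

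Section 3.4 also asks that other eligibility laboratory limits be met, and the beta-hCG is listed under laboratory tests in 2.2. The more natural reading is the organ and marrow limits of 2.1.1.8, since pregnancy is a separate exclusion. Even the generous reading would place a test only between courses.

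Contraception is mandatory, a physical examination is due within 4 days of each cycle, and nothing prevents testing when it is clinically indicated. These points lower the risk and weigh against a high severity. None is a scheduled test, and the protocol requires one at entry despite the same contraception rule.

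The consent pages, and some text after the Appendix 7 laboratory list, were not available. A repeat test could be mentioned there, so the finding covers the available text only.

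**Conclusion.** The gap is real and narrow. In the available text, one pregnancy test is scheduled before cycle 1 and none after it, although treatment is open-ended and pregnancy requires immediate discontinuation. The gap is clearest for cycles 2 and 3 of a course, where the condition in 3.4 does not apply.

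A reader might infer from the 14 of 21 infusions that fetal exposure is likely or that many patients are at risk. The documents do not support that. The figure restates the schedule for a woman who completes course 1, earlier patients averaged fewer than two cycles, and few women of child-bearing potential, possibly none, may enroll. Nor does the point touch the response endpoint, the two-stage decision rule or its error rates. It is a low-frequency patient-safety matter, and the case for acting is that the harm is serious and the remedy costs very little. The conclusion assumes that the text not available contains no repeat test.

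**What to change.** In 3.5.2 and Appendix 2, repeat the urine or serum beta-hCG for women of child-bearing potential within 2 days before day 1 of every cycle, with the draws already due then. Add to 3.5.2:

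- A positive result holds dosing until pregnancy is confirmed, in which case 3.6.1 and 7.3.2.1 apply, or excluded.
- Where a tumor source of hCG is already documented, as can happen with the germ cell tumors eligible under 2.1.1.1, the investigator excludes pregnancy by another clinical means, such as ultrasound or the hCG trend. Each expected positive then does not start a new hold.

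Section 3.4 needs no change. Within a course, the +7-day window in 3.2 already allows a short work-up. Between courses, restaging falls two weeks (+12/-3 days) after the course. Counted from the last infusion of cycle 3, that is day 7 + 11 = 18 to day 7 + 26 = 33, so a fixed 28-day ceiling on the work-up would conflict with timing the plan already permits.

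The cost is one inexpensive test per cycle in a few patients, with no added visit. The downside is an occasional false-positive work-up that may delay a cycle by a few days.

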### 2.3 REGISTRATION PROCEDURES

Authorized staff must register an eligible candidate with NCI Central Registration Office (CRO) within 24 hours of signing consent. A registration Eligibility Checklist from the web site (<http://home.ccr.cancer.gov/intra/eligibility/welcome.htm>) must be completed and send via encrypted email to: NCI Central Registration Office [[contact]](mailto:[contact]). After confirmation of eligibility at Central Registration Office, CRO staff will call pharmacy to advise them of the acceptance of the patient on the protocol prior to the release of any investigational agents. Verification of Registration will be forwarded electronically via e-mail to the research team. A recorder is available during non-working hours.

#### 2.3.1 Treatment Assignment Procedures (For registration purposes only)

##### Cohorts

Number	Name	Description
1	Primary thoracic malignancy	Patients with primary thoracic malignancy with favorable ABCB4/ABCB11/RALBP/CYP8B1 genotypes
2	Metastatic extra-thoracic malignancy	Patients with extra-thoracic malignancy metastatic to lungs, pleura or mediastinum with favorable ABCB4/ABCB11/RALBP, CYP8B1 genotypes
3	Thoracic malignancy, primary or metastatic -no genotyping (Closed)	Subjects enrolled without regard to ABCB4/ABCB11 genotypes

##### Arms

Number	Name	Description
1	Mithramycin	Single agent IV mithramycin.

## **Arm Assignment**

Patients in cohorts 1 and 2 will be directly assigned to arm 1.

The 12 patients in cohort 3 were directly assigned to arm 1. Cohort 3 is now closed.

## **3 STUDY IMPLEMENTATION**

### **3.1 STUDY DESIGN**

This study will be conducted as a single site, phase II trial utilizing a Simon Optimal Design. Patients will be analyzed in two cohorts on the basis of primary thoracic malignancy vs. extra-thoracic malignancy metastatic to lungs, pleura or mediastinum. The goal of the study is to determine response rates, pharmacokinetics and molecular responses following 6h mithramycin infusions as a prelude to combinatorial studies as well as protocols utilizing 24h continuous infusions targeting pharmacodynamic endpoints in tumor tissues.

Patients will undergo eligibility evaluation in the Thoracic Surgery Clinic (OP-3). Patients deemed eligible for therapy will sign an informed consent and receive mithramycin as described in Section 3.2. Patients may continue to receive mithramycin as long as they tolerate drug and do not have progressive disease (Section 6.4).

Patients on study will be closely monitored for the development of toxicities using regular physical examinations, blood pressure monitoring, and laboratory evaluations with particular attention to the development of any signs of bleeding. Patients will be admitted to the hospital for the first treatment cycle to allow for close monitoring of toxicities. For subsequent cycles, local patients may receive infusions in the day hospital; patients traveling from out-of-town will be admitted to the hospital. Two weeks (plus 12 or minus 3 days) following each course of therapy (three 21-day cycles) patients will undergo appropriate staging studies to determine response to therapy using RECIST criteria.

### **3.2 DRUG ADMINISTRATION**

Given our recent findings pertaining to ABCB4, ABCB11, RALBP and CYP8B1 SNPs that distinguish patients who did and did not experience mithramycin-mediated hepatotoxicity on this trial, the protocol has been amended to accrue only those patients with favorable ABCB4/ABCB11/RALBP/CYP8B1 genotypes. Fourteen of these patients (7 with primary thoracic malignancies and 7 with extrathoracic malignancies metastatic to the chest) will receive mithramycin infusions during cycle 1 at 30mcg/kg per day. Those patients tolerating 30 mcg/kg infusions during the first cycle will receive subsequent cycles of mithramycin at a dose of 50 mcg/kg using the same infusion schedule. Based on the PK data obtained on this trial to date, this dose of mithramycin would be expected to produce Cmax of ~40nM and steady state levels of ~20-25nM, concentrations approximating lowest therapeutic doses in preclinical tissue culture experiments. Patients exhibiting dose-limiting toxicities during cycle 1 will receive subsequent infusions at a dose of 25mcg/kg, with dose reduction guidelines listed in section 3.3. If one or more patients in each cohort exhibit response to therapy, an additional 14 patients will be accrued to the respective cohort(s) to further define response rates Simon Second Stage). Drug administration in the Second Stage will be identical to that in the First stage.

Mithramycin will be administered intravenously via central line over 6 hours once daily for 7 days to be repeated every 21 days (+7 days/-3 days). Three cycles will constitute one course. Intravenous hydration will be provided as clinically indicated.

**Note:** At least 23 hours should elapse between the beginning of one infusion and the beginning of the next.

